6.5 Withdrawal Procedures

Protocol-specified withdrawal procedures are the same as those to be performed at the last study visit (Section 6.2.9).

6.6 Subject Replacement

Subjects who prematurely discontinue the study will not be replaced. Up to 15 subjects will be enrolled to ensure 10 subjects complete the trial.

6.7 Subject Re-screening

Subjects previously denied entry into the study may be re-screened for enrollment once all inclusion (Section 4.2) and no exclusion criteria (Section 4.3) are met.

7 STUDY TREATMENT

7.1 Formulation

The product ingredients are consistent with other retail and OTC products at acceptable concentrations.

Formulation information is presented below in Table 7-1.1

Table 7-1. Santalis Mouth Rinse

Active ingredient	0.5% EISO
Inactive ingredients	Polysorbate-80 NF, Poloxamer 407 NF, Xylitol NF, Sorbitol 70% Solution USP, Menthol USP, Peppermint Oil NF, Sodium Saccharin USP, Purified Water USP
Dosing schedule	30 mL to be used thrice daily for approximately 10 weeks or until mucositis resolves.
Manufacturer	Pam Lewis and Associates, Boerne TX
Packaging	1 Liter bottles
Storage requirements	Store at controlled room temperature ^a (20°C to 25°C [68°F to 77°F])

a: Controlled room temperature indicates a temperature maintained thermostatically that encompasses the usual and customary working environment of 20°C to 25°C (68°F to 77°F). Excursions are allowed between 15°C and 30°C (59°F and 86°F).

7.2 Packaging and Labeling

The study product labels will contain, at minimum, the following information:

- Sponsor name and address;
- Protocol number;
- Subject number (may be hand printed on the label);
- Product description;
- Lot number;
- Storage conditions;
- Expiry or retest date, if applicable;
- "Investigational use only. Keep out of reach of children"

Study product(s) will be provided in study kits containing the mouth rinse.

7.3 Dosing Regimen

Subjects are to administer the treatment regimen according to the following schedule and order:

The following treatment products will be provided:

- Mouth Rinse— Take 30 ml by mouth each time. Swish for 30 seconds and spit. Use the rinse three times daily, including weekends when radiotherapy is not delivered, ideally 15 minutes after meals and refrain from eating or drinking for one hour after rinsing.

The investigational products contain ingredients commonly found in other oral products. The site staff will initially be responsible for teaching how to use SAN005, and then the subject will be instructed on the procedure for self- administration at home.

Subjects will be supplied with a patient dosing diary during the treatment period and will be instructed to answer several questions about their experience with the treatment regimen. The investigator or designee should collect and review the diary with the subject at every visit.

7.3.1 Dose Modification

In the event a subject experiences any health issue in the treatment area during the study, the subject should be examined by the study physician. All AEs should be recorded in the case report forms (CRFs) and any reactions to study product must be reported to the study coordinator.

If a subject experiences an allergic reaction to the study drug oral diphenhydramine may be administered according to package labeling if necessary.

Upon resolution of any reaction (localized or generalized), the subject may be re-challenged with study treatment at the discretion of the treating physician after careful analysis of the possible cause of the reaction. The investigator or designee must stress the importance of using the study treatment according to the instructions provided. In the absence of further reactions, study treatment may resume. If a reaction recurs, treatment should be stopped. Subjects should report to the study physician, and they will be discontinued from the study.

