6.3 Interruption or Discontinuation of Treatment

Every subject has the right to refuse further participation in the study at any time and without providing reasons (see also Section 8.1.2). A subject's participation is to be terminated immediately upon his/her request. The investigator should seek to obtain the reason and record this on the case report form (CRF).

Should the subject, during the course of the study, develop conditions which would have prevented his/her entry into the study according to the safety related medical exclusion criteria, he/she must be withdrawn immediately.

The subject may be withdrawn from the study at any time at the discretion of the investigator for medical reasons and/or due to non-adherence to the treatment scheme and other duties stipulated in the study protocol. The reasons are to be fully documented on the CRF.

In addition, the sponsor and the investigator reserve the right to end or suspend the study at any time (see Section 8.2.3).

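### Section 7.3.1 allows re-challenge after a resolved allergic or generalized reaction, and no finding about the cause rules it out; Section 6.3 on its natural reading would withdraw a subject judged hypersensitive to the product

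*Combined protocol and SAP*

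**What the plan says.** Section 7.3.1 (Dose Modification) opens its treatment of allergy with "If a subject experiences an allergic reaction to the study drug" and offers oral diphenhydramine if needed. The next paragraph sets the re-challenge rule: "Upon resolution of any reaction (localized or generalized), the subject may be re-challenged with study treatment at the discretion of the treating physician". The condition attached is that this happens "after careful analysis of the possible cause of the reaction". If no further reaction follows, treatment may resume. The mandatory stop is: "If a reaction recurs, treatment should be stopped"; the subject then also leaves the study.

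Section 6.3 covers a subject who develops, during the study, a condition that would have kept him or her out "according to the safety related medical exclusion criteria, he/she must be withdrawn immediately". It does not list which exclusion criteria it means. Exclusion criterion 3 in Section 4.3 bars anyone with a known sensitivity to a constituent of the product. Section 6.3 also has a discretionary exit: "The subject may be withdrawn from the study at any time at the discretion of the investigator for medical reasons". Section 6.4 lists adverse events among the reasons that justify stopping.

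Section 7.8.1.2 has the investigator rate each adverse event's relationship to the product under Table 7-8.

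**The concern.** A subject may have a generalized allergic reaction that resolves and that the physician, after the required analysis, believes the rinse caused. Section 7.3.1 still lets that subject be given the rinse again, because no outcome of the analysis closes off the option. The section's own compulsory stop depends on a second reaction, so it acts only after re-exposure.

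Section 6.3 appears to point the other way for the same subject. Staff managing a reaction would naturally open the dose modification section, and nothing there sends them to Section 6.3. At stake is avoidable re-exposure to a suspected allergen in a small proof-of-concept study. This is a matter of subject safety, not of estimation.

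**Working it through.** The plan gives no figure on this point to reproduce, so the main check sets the rules side by side. A short calculation of size follows.

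1. **Scope of the permission.** The re-challenge sentence covers every resolved reaction, localized or generalized, and directly follows the paragraph on allergic reactions. It makes no exception for type, severity, seriousness or attributed cause. No other section restricts re-challenge.

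2. **What could bar re-exposure under 7.3.1.** There are three conditions: resolution, analysis of the cause, and a physician's decision. The first says nothing about cause. The second has no stated consequence. The third is discretionary.

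3. **What 6.3 would require.** Two inferences are needed to reach mandatory withdrawal. First, criterion 3 must count as a safety-related medical exclusion; 6.3 does not say so, but product sensitivity is a natural member of that group. Second, a reaction judged to be hypersensitivity must count as a known sensitivity. A reaction merely rated as drug-related is not enough, because Table 7-8 grades causal likelihood and not mechanism.

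4. **Whether the cause can be judged before re-challenge.** It can. Probably related in Table 7-8 needs reasonable timing, no other likely cause and a reasonable response when the product is withdrawn. All three can be known before re-exposure. Only the Definitely related row mentions re-challenge, and only as an example of evidence.

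5. **Who decides, and in what order.** The investigator gives the causality rating (7.8.1.2); the treating physician decides on re-challenge (7.3.1). They may be the same person. No step requires the rating to come first.

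6. **Other exits.** The further provision in 6.3 is permissive ("The subject may be withdrawn from the study at any time at the discretion of the investigator for medical reasons"). The adverse event item in 6.4 turns on the investigator's judgement.

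7. **Dose and setting.** Section 7.3.1 sets no dose, place or observation period for the re-challenge. Routine use in 7.3 is "Take 30 ml by mouth each time", three times daily, and after initial teaching "then the subject will be instructed on the procedure for self- administration at home".

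**Size.** Let p be the chance that a subject has an allergic or hypersensitivity reaction attributed to the product. The documents give no value, so p is assumed to lie between 0.5% and 5%; known sensitivity is already excluded at entry. Planned enrolment is up to 15 (Sections 6.6 and 8.1). The chance of at least one case is 1 − (1 − p)^15:

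- p = 0.005: 1 − 0.995^15 = 7.2%
- p = 0.01: 1 − 0.99^15 = 14.0%
- p = 0.02: 1 − 0.98^15 = 26.1%
- p = 0.05: 1 − 0.95^15 = 53.7%

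This is the chance that the situation arises. The chance that a physician then re-exposes the subject, or that harm follows, cannot be larger and is not estimated here.

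**The case against.** The strongest reply is that the two sections can be read together. Section 7.3.1 grants a permission and 6.3 imposes a duty, and a permission does not ordinarily override a duty. If the analysis points to product sensitivity, 6.3 ends participation; if it does not, 7.3.1 applies. This stands. A reader might infer that the protocol flatly contradicts itself, or that it directs staff to re-expose allergic subjects; the text supports neither. But 7.3.1 does not state the reconciliation, and it depends on an unstated reading of which criteria 6.3 covers.

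Safeguards also exist. A physician must decide, the cause must be considered, reactions must be reported to the coordinator, subjects are seen weekly during radiotherapy (6.2.2), and serious events go to the sponsor within 24 hours (7.8.1.3). These lower the risk but set no bar.

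Three stronger readings should be resisted:

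- **Re-challenge means a full dose at home.** Section 7.3.1 separates re-challenge from resumption of treatment, so the routine regimen cannot simply be carried into the re-challenge step. The text only leaves dose and setting open. The product is also a 0.5% rinse that is spat out, not swallowed.
- **Every generalized reaction rated Probably related falls under 6.3.** Such a reaction need not be hypersensitivity, and criterion 3 concerns sensitivity to constituents.
- **The 7% to 54% range is a risk of harm.** It rests on assumed rates and bounds only the triggering event.

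**Conclusion.** The point holds as a gap in a stated safety rule. Section 7.3.1 permits discretionary re-exposure after a resolved allergic or generalized reaction whatever the cause analysis finds, and compels a stop only on recurrence. That part rests on the text of 7.3.1 alone. The tension with 6.3 is an inference: it requires criterion 3 to be a safety-related medical exclusion and the reaction to be judged hypersensitivity to the product.

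On the assumed rates, the chance that any of 15 subjects meets the situation is 7% to 54%, so it may well not occur. Local mucosal reactions that radiotherapy or chemotherapy could explain are outside the point unless they are judged to be hypersensitivity to the product. No bias in the efficacy results is claimed. The change is worth making because the possible harm is avoidable and the remedy is small. Confidence is medium, mainly because 6.3 does not name its criteria.

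**What to change.** In Section 7.3.1:

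1. State that an allergic or hypersensitivity reaction, localized or generalized, that the investigator judges at least possibly related to the product and that has no other established cause leads to permanent discontinuation of study drug under 6.3, with no re-challenge.
2. Limit discretionary re-challenge to resolved reactions judged not to be hypersensitivity to the product, for example local mucosal irritation explainable by radiotherapy or chemotherapy.
3. Require that judgement to be recorded before any re-challenge.

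Items 1 and 2 should turn on the same question, whether the reaction is hypersensitivity to the product, so that an allergic reaction rated only Possibly related does not fall between them.

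In Section 6.3, name exclusion criterion 3 as a safety-related criterion and refer to 7.3.1.

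The cost is a few sentences and one cross-reference. No visit, assessment or form is added, because the causality rating is already required for adverse events. The downside is possibly one fewer subject continuing on treatment: 1 of up to 15 enrolled, or 1 of the 10 completers sought.

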7.3.2 Assignment to Treatment

This is an open label study and all subjects will receive the active study medication. No randomization is required.

7.3.3 Subject Numbering

Each subject who signs an informed consent form and successfully completes the screening procedures will be enrolled in the study. Each subject will be assigned a unique subject number that will be written on the products and used on all CRFs.

7.4 Prior and Concomitant Therapy

All medications, including over the counter (OTC) drugs, mouth washes or rinses, taken within 30 days prior to the start of the study will be recorded at Pretreatment Visit (Visit 1). Information regarding the total daily dose, route of administration, start and discontinuation dates, and indication are to be recorded on the subject's CRF.

7.5 Treatment Compliance

Records of study product used and intervals between visits will be kept during the study.

Product accountability will be noted by the study monitor during site visits and at the completion of the trial.

Subjects will be asked to return all partially used and empty products to the study site at each visit. The products will be weighed prior to dispensation and at each study visit and the weight difference will be analyzed as a measure of product usage. Subjects who are consistently noncompliant (ie, < 80% of required doses) will be counseled and may be withdrawn from the study. Subjects will be asked to return all unused product at the end of the study.

7.6 Efficacy Assessment

Efficacy is assessed by the patient's self-reporting of pain using Numerical Rating Pain Scale (NRPS) and the physician's assessment of oral mucosal changes using RTOG grading of mucositis.

7.6.1 Pain Assessment

At each Study Visit the NRPS will be recorded for mouth pain and pain upon swallowing. For the primary efficacy assessment the NRPS scale at baseline will be compared to Week 5. Subjects that complete at least 80% of treatments as determined by the diary and confirmed by the weight of the returned study product will be included in the efficacy analysis.

If possible, the same investigator who completes the scoring at Baseline should complete all subsequent assessments for the patient.

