3. STUDY PLAN

3.1 Overall Study Design

This trial will be a single-center, open-label, proof of concept trial to evaluate the efficacy, safety and tolerability of SAN005 treatment regimen when administered to adults at least 18 years of age for the prevention and treatment of oral mucositis.

Subjects will enter the Screening Period once the informed consent process has been completed. Subjects who are scheduled to receive radiation with or without concurrent chemotherapy and meet all of the inclusion criteria and none of the exclusion criteria will be eligible for the study:

Once subject eligibility is confirmed the subject will start SAN005 treatment on Day 1 of their radiation treatment. All subjects will receive active medication in the study with the first dose administered on Day 1.

Subjects will be instructed on the administration of study medication thrice daily till oral mucositis resolves. Subjects will return to the clinic once a week while receiving radiation and then once every two weeks once their radiation has been completed and then until their mucositis has resolved for the Final Study Visit.

Preliminary Efficacy Evaluation will be the severity of pain rated by the NRPS and mucositis grade by RTOG criteria at Visit 7 (Day 36). Additional secondary efficacy evaluations will include the severity of pain rated by the NRPS and mucositis grade by RTOG criteria at each study visit, frequency of the PEG tube for feeding during the duration of treatment and weight loss from baseline through Visit 5 and 7. The time of mucositis onset and duration will also be used in assessing efficacy. Additional secondary and exploratory endpoints will be outlined in the statistical analysis plan. The overall efficacy is determined by comparing the data to historical controls.

Safety will be assessed by evaluating adverse events (AEs) with respect to severity, duration, and relationship to study drug. In addition tolerability evaluations will be performed at each study visit.

During the active treatment period, subjects will return to the study site according to the study schedule for interim assessments, review of subject dosing diaries, and assessment of concomitant medication and adverse events (AEs).

The study design is summarized in Figure 3-1.

Figure 3-1 **Study Design**

Pretreatment	Treatment		Follow-up
Day 0	Day 1 Baseline	Day 8,15,22,29,36,43 (\pm 2 day, weekly)	Every other week until mucositis resolves or it reaches Visit 10

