3.2 Study Endpoints

Primary efficacy will be assessed by the numerical rating pain scale (NRPS) and RTOG mucositis grade at Visit 7 (Day 36).

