4.2 Inclusion Criteria

Patients will be included in the trial if they meet all of the following criteria:

1. Subjects with head and neck cancer involving the oropharynx or oral cavity, who are expected to undergo high dose radiation therapy (i.e., ≥ 60 Gy) that typically results in oral mucositis, with or without concurrent chemotherapy or biologic targeted therapy.
2. At least 18 years of age
3. Estimated survival of at least 6 months.
4. No prior radiation therapy to the head and neck area, and no chemotherapy within the last year except for induction chemotherapy delivered (or to be delivered) prior to the current course of radiation therapy
5. Female subjects of child-bearing potential must agree to use an adequate form of contraceptive (e.g., hormonal, barrier method or abstinence) prior to study entry and for the duration of the trial.
6. Are willing to refrain from using other treatments for oral mucositis until they consult with the study investigator(s).
7. Are able to give written informed consent in a manner approved by the Institutional Review Board and comply with the requirements of the study.

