4.3 Exclusion Criteria

Patients will be excluded from the trial if they meet any of the following criteria:

1. Have preexisting mucositis from other causes.
2. Are immunosuppressed or in chronic use of immunosuppressive drugs.
3. Have a known sensitivity to any of the constituents of the test product including sensitivities to sandalwood oil, fragrances or any member of the Compositae family of vascular plants (e.g., sunflowers, daisies, dahlias, etc.).
4. ECOG performance status ≥ 3
5. Unwilling or unable to follow the protocol requirements.
6. Have any condition that in the opinion of the investigator would confound the efficacy,

safety and tolerability assessments, such as oral thrush.

7. Have participated in any clinical trial in the previous 30 days.
8. Are pregnant, breastfeeding, or unwilling to practice an acceptable form of birth control during the study.

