8. STATISTICAL METHODS AND DETERMINATION OF SAMPLE SIZE

8.1 General Considerations for Data Analysis

All statistical processing will be performed using the SAS® system (Version 9.12 or higher). Up to 15 subjects will be enrolled in this study to ensure a minimum of 10 subjects complete the study. The primary efficacy analysis of the study will be the determination of the NPRS from baseline to Visit 7 (Day 36).

Secondary efficacy endpoints will be evaluated using descriptive statistics. No interim or subgroup analyses are planned.

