8.5.4 Efficacy Analysis

The primary data analysis set for efficacy analyses will be the PP defined in Section 8.4.3. The primary analysis will be the determination of the severity and intensity of mucositis from Baseline to Visit 7 (Day 36).

The secondary efficacy endpoints analysis will be summarized using standard statistical methods and outlined in the Statistical Analysis Plan (SAP). In general, categorical endpoints will be tabulated by number, percentage, and a 95% 2-sided confidence interval (exact methodology) will be estimated. Continuous endpoints (i.e., percent change from baseline) may be summarized using descriptive statistics (N, mean, median, standard deviation, and range).

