Appendix 2 - RTOG Grading Scales for Acute Radiation Mucositis

Grade	Mucous Membrane
0	No change over baseline
1	Injection/may experience mild pain not requiring analgesic
2	Patchy mucositis which may produce an inflammatory serosanguinitis discharge/may experience moderate pain requiring analgesia
3	Confluent fibrinous mucositis/may include severe pain requiring narcotic
4	Ulceration, hemorrhage or necrosis

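### The primary comparison in 7.6.1 is with the subject's own baseline, which alone cannot show prevention, and nothing links it to the historical comparison that 3.1 says determines efficacy

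*Combined protocol and SAP*

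**What the plan says.** Three sections describe the primary efficacy comparison as one from baseline to the fifth week.

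- 7.6.1 is the most explicit: "For the primary efficacy assessment the NRPS scale at baseline will be compared to Week 5".
- 8.1 agrees in substance: "The primary efficacy analysis of the study will be the determination of the NPRS from baseline to Visit 7 (Day 36".
- 8.5.4 uses the same time frame but a different variable, mucositis rather than pain: "The primary analysis will be the determination of the severity and intensity of mucositis from Baseline to Visit 7 (Day 36".

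Section 3.1 names another comparator: "The overall efficacy is determined by comparing the data to historical controls". Section 3.2 gives the endpoints and the visit but no comparator: "Primary efficacy will be assessed by the numerical rating pain scale (NRPS) and RTOG mucositis grade at Visit 7 (Day 36".

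Section 8 contains no reference to historical controls. No section gives a historical source, a historical value or a rule for declaring benefit, and none says how the baseline comparison relates to the historical one. Sections 3.1 and 8.5.4 defer secondary and exploratory endpoints to a statistical analysis plan. Neither says that plan will settle the primary comparison.

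**The concern.** The trial has one arm, and SAN005 starts on the first day of radiation. Section 4.3 excludes subjects who "Have preexisting mucositis from other causes", and 4.2 selects subjects for "high dose radiation therapy (i.e., ≥ 60 Gy) that typically results in oral mucositis". Mouths are therefore expected to get worse between baseline and Day 36 whether or not the product works. A comparison with the subject's own baseline has no value that stands for no SAN005 effect.

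The efficacy objective in Section 2 covers prevention as well as treatment. If the comparison that 7.6.1 labels primary is read on its own, the trial cannot answer the prevention part. If 3.1 governs, Section 8 does not describe the analysis that decides efficacy. Which comparison the conclusion rests on could then be settled after the data are seen.

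**Working it through.** **The plan's own figures.** Sections 4.1 and 8.1 plan 15 enrolled to obtain 10 completers. This allows for a loss of 5/15 = 33.3%, and 10 / (1 − 1/3) = 15. Neither number comes from either comparison: 8.2 disclaims any power basis, and no effect size, SD or error rate is given. There is nothing further to reproduce.

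**Same time point.** Day 36 = 1 + 5 × 7, so Week 5 in 7.6.1 and Visit 7 (Day 36) elsewhere are the same visit. The comparisons differ only in what that visit is compared with.

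**What each comparison estimates.** Let B be the baseline mean, V the Visit 7 mean on SAN005 and H the historical Visit 7 mean. Let r be the rise that radiation would cause without the drug, and d the drug effect (negative means benefit).

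- Within-subject: V − B = r + d. With no drug effect this equals r, not 0.
- Historical: V − H. If the historical patients are comparable, this equals d.
- The first is positive and the second negative whenever B < V < H. No test is needed for that reversal.

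**RTOG.** Appendix 2 defines grade 0 as "No change over baseline". Change from baseline on this scale is therefore zero or worse, whatever the product does. This follows from the documents alone.

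**NRPS, an illustration with assumed values.** Take n = 10, SD 2 for both comparisons, B = 1, H = 6 and an error-free historical mean. The 95% half-width is t(0.975, 9) × SD / √n = 2.262 × 2 / √10 = 1.43.

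- A 2-point benefit (V = 4): against baseline, 4 − 1 = +3.0 (1.57 to 4.43); against history, 4 − 6 = −2.0 (−3.43 to −0.57).
- No effect (V = 6): against baseline, 6 − 1 = +5.0 (3.57 to 6.43); against history, 0.0 (−1.43 to 1.43).

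Both products show a rise from baseline. Only the external reference separates them.

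**How often both intervals would exclude zero in opposite directions.** This was simulated with 100,000 trials of n = 10 per setting, baseline SD 1.5, Visit 7 SD 2, correlation 0.3, scores rounded and limited to 0–10, a fixed historical mean and a 2-point benefit. All these inputs are assumptions.

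| Baseline mean | Historical mean 5 | Historical mean 6 |
|---|---|---|
| 0.5 | 70.7% | 79.1% |
| 1 | 57.4% | 77.4% |
| 2 | 16.8% | 56.9% |
| 3 | 0.9% | 16.2% |

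At baseline mean 1 and historical mean 6, changing one input at a time lowers the 77.4% further:

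- a 1-point benefit: 29%
- Visit 7 SD 2.5: 56%
- Visit 7 SD 3: 39%
- historical mean estimated from 10 controls: 54%

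**The historical comparison also lacks an input.** Suppose 4 of 10 subjects reach RTOG grade 3 or higher (exact 95% interval 12% to 74%). Against an assumed fixed historical rate of 60%, 70% or 80%, the probability of 4 or fewer is 0.166, 0.047 or 0.006. The reading depends on a rate that the plan does not give.

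**The case against.** The best reply is that the passages work in layers: 3.2, 7.6.1 and Section 8 define what is measured in each subject, and 3.1 says how those data are then judged. On that reading, change from baseline is the outcome and history is the comparator, so there is no conflict. The reading is reasonable, and it means the sections need not be treated as irreconcilable rivals. It does not remove the point, because no passage states it and 7.6.1 names baseline itself as what Week 5 is compared with.

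The support from 8.5.4 is also weaker than it looks. Its variable is mucositis, and RTOG grade is already expressed relative to baseline, so the baseline wording there may add nothing to the Visit 7 grade in 3.2. The case rests mainly on 7.6.1, with 8.1 behind it.

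A reader might go further and infer that following Section 8 would lead to a report of statistically significant worsening for an effective product. The documents do not support that. Section 8 names no test for the primary analysis; its one inferential tool is an exact interval for categorical endpoints, in a paragraph on secondary endpoints. The t intervals above are illustrations added here. A descriptive rise in pain during radiation would not naturally be read as evidence against the product.

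It is also true that NRPS can fall. Section 4.3 excludes mucositis from other causes, not tumour pain, so entry scores may be well above zero.

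**Conclusion.** The point stands in this form. The comparison labelled primary in 7.6.1 cannot by itself show whether SAN005 prevents mucositis, and the plan does not connect it to the historical comparison that 3.1 says determines efficacy. For RTOG this needs no assumed numbers. It needs only the single-arm design, the start on Day 1 of radiation and the definition of grade 0. For NRPS the two comparisons oppose each other in direction whenever the Visit 7 mean lies between a lower baseline mean and a higher historical mean.

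The size is not established. It would be tempting to quote the simulated 77% as the chance of opposite conclusions, but the documents supply none of its inputs, and within the settings shown the rate runs from 0.9% to 79.1%. It should be read only as showing that reversal is possible and depends strongly on entry pain.

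**What to change.** In 7.6.1, 8.1 and 8.5.4, consistently with 3.1 and 3.2, state that efficacy is judged by comparing the SAN005 result at Visit 7 (Day 36) with a historical-control value fixed, together with its uncertainty, before the data are seen. Either form would do, provided one is chosen in advance:

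- the Visit 7 value against the historical Visit 7 value; or
- the change from baseline against the corresponding historical change, which takes account of entry pain but needs a source that reports baseline as well.

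The references to baseline in 8.1 and 8.5.4 therefore need not be deleted, provided the historical comparator is added. Say in 7.6.1 that the within-subject change to Week 5, presented on its own, describes the course under radiation and is not used to judge efficacy.

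This needs no extra subjects or visits, but it is more than a wording change. A historical value must be found, justified and recorded in advance, as 3.1 already implies. The efficacy claim would then rest openly on a non-randomised comparison.
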